### **Rationale for Omadacycline Dose Regimen Selection:**

The dosing regimen of omadacycline selected for this study is based on the nonclinical and clinical experience to date, including *in vitro* antibacterial activity, PK characteristics, clinical efficacy in prior studies, and the overall safety and tolerability profile. Key considerations in dose selection are summarized below:

- In PTK0796-SDES-0501, the PK of omadacycline iv were linear over the entire dose range (25 mg to 600 mg) as assessed by area under the concentration time curve (AUC). Therefore, the loading dose given on Day 1 in the pivotal Phase 3 trials, 100 mg iv every 12 hours (q12h), is from an exposure perspective comparable to the 200 mg iv loading dose on Day 1 to be utilized in this study.
- In PTK0796-MDES-0601, 200 mg iv for seven days was safe and well tolerated. Alanine aminotransferase (ALT) was reported as increased in 26% of subjects however the post-baseline change was approximately 30 IU/L on the last day of infusion. A heart rate model demonstrated that the post-baseline increase in heart rate for a 200 mg dose could be minimized to 15 beats per minute with infusion over 60 minutes.
- In PTK0796-UUTI-15103, omadacycline dosed as 200 mg iv on Day 1 followed by 300 mg po daily for 5 days, 300 mg po q12h on Day 1 followed by 300 mg po daily for 5 days and 450 mg po q12h on Day 1 followed by 450 mg po daily for 5 days demonstrated high urinary concentration on Day 1 and Day 5. For the 200 mg iv load

followed by 300 mg daily dosing group, mean urinary concentrations ranged from 22 to 65 µg/mL on Day 1 and 21 to 42 µg/mL on Day 5. For the 300 mg dosing group, mean urinary concentrations ranged from 14 to 20 µg/mL on Day 1 and 17 to 30 µg/mL on Day 5. For the 450 mg dosing group, mean urinary concentrations ranged from 11 to 25 µg/mL on Day 1 and 30 to 48 µg/mL on Day 5.

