#### Table 3Scheduled Study Visits

Study Day is calculated relative to the first dose of test article (Day 1); there is no Day 0 – the day prior to the first dose of test article is Day -1. If no test article is taken, study day is calculated relative to the date of randomization.

For efficacy outcomes, the data collected at the EOT, PTE and FFU visits, regardless of when these occur will be utilized in the analysis in the ITT and micro-ITT population. The CE and ME populations exclusions due to windowing are outlined in Sections 4.4 and 4.5.

For each safety outcome and UTISA data, analyses will utilize assessments occurring during the scheduled visit windows (provided in Table 3). Thus, if a subject has a visit outside the scheduled visit window, for example, a PTE Visit occurred 20 days after the subject's first investigational product dose, the assessment will not be summarized with the PTE Visit but will be considered an unscheduled assessment. If a subject does not have an assessment at a scheduled visit and an unscheduled assessment was taken within the window for the time point (for example, 21 days ( $\pm$  2 days) after the subject's first day of therapy for PTE), these assessments will be summarized in the by time point analyses. If more than one measurement is

93 Version: 1.0 Status: Approved Approved Date: PTK0796-AP-17202 Statistical Analysis Plan

Omadacycline (PTK 0796)

PTK0796-AP-17202 Statistical Analysis Plan

taken during the visit window, the value taken on the scheduled visit will be utilized or if no scheduled visit was done, the first (earliest) measurement in the visit window will be used. If more than one measurement is taken on the same day, the assessment closest to the start of the dose will be used for on treatment values and the last measurement on the day will be used for post-treatment values. For worst overall post-baseline analyses, all assessments including those obtained from unscheduled visits will be included.

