The number and percentage (based on the number of subjects with a normal level at baseline) of subjects in each treatment group with an elevated transaminase level (> 3 × upper limit of normal [ULN], > 5×ULN, and > 10 × ULN), an elevated bilirubin level (> 1.5 × ULN and > 2 × ULN) will be presented by study visit. A listing of subjects who meet the laboratory criteria for Hy's law at the same visit will also be provided. The laboratory criteria for Hy's law is defined as 1) ALT or AST> 3 × ULN, ALP  $\leq$  2.0 × ULN, and total bilirubin > 1.5 ULN and 2) ALT or AST> 3 × ULN, ALP  $\leq$  2.0 × ULN, and total bilirubin > 2 × ULN

Tabulated results of urine dipstick tests for leukocyte esterase and nitrates will be summarized by treatment group across visits and will include descriptive statistics for the microscopic evaluations for white blood cells.

Subject listings of all laboratory data (local and central laboratory data) collected during the study will be provided, including calculated CrCl (using the Cockcroft-Gault equation). Laboratory values outside normal limits will be identified in the subject data listings with flags for low (L) and high (H) as will laboratory values that meet the clinically notable (CN) thresholds.

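### The liver threshold table has no overall post-baseline row, and the Hy's law listing cannot pick up ALT/AST and bilirubin peaks that fall at different visits

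*SAP*

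**What the plan says.** **Threshold table (SAP 8.5).** The transaminase and bilirubin counts "will be presented by study visit", with a denominator "based on the number of subjects with a normal level at baseline". No overall row is specified.

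**Hy's law listing (SAP 8.5).** Two criterion sets are given. Both need ALT or AST >3×ULN and ALP ≤2×ULN; one adds bilirubin >1.5×ULN, the other >2×ULN. The listing covers subjects who meet Hy's "law at the same visit will also be provided".

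**Which values feed a by-visit table (SAP 5.4 and 8.5).** For safety outcomes, "analyses will utilize assessments occurring during the scheduled visit windows". An unscheduled value inside a window counts when the scheduled assessment is absent: "these assessments will be summarized in the by time point analyses". With several values in a window the scheduled one is used, and "if no scheduled visit was done, the first (earliest) measurement in the visit window will be used". SAP 8.5 adds that a central value takes precedence over a local one in the same window.

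**Worst-value rule (SAP 5.4).** "For worst overall post-baseline analyses, all assessments including those obtained from unscheduled visits will be included". SAP 8.5 confirms that central and local values both count, and SAP Appendix 2 takes the highest value as worst for ALT, AST and bilirubin.

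**Related commitments.** Protocol 12.6.1 promises clinically notable laboratory values both by visit and for the overall worst post-baseline value. SAP 8.6 gives vital signs an overall post-baseline incidence of clinically notable values.

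**The concern.** The natural safety question for a liver signal is how many subjects in each arm ever exceeded a given multiple of ULN, and whether anyone had both a transaminase and a bilirubin rise. A by-visit table does not answer the first part, and a same-visit listing answers the second only for concurrent rises.

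This matters somewhat more than usual here. The study compares 100 mg and 200 mg iv regimens, SAP Table 12 says it is to inform dose selection for a possible Phase 3 program, and the protocol's dose rationale says of an earlier seven-day 200 mg iv study: "Alanine aminotransferase (ALT) was reported as increased in 26% of subjects". Arms are small, so a few uncounted crossings could alter the comparison between regimens.

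**Working it through.** The plan gives no figure to reproduce. The check sets the rules side by side, with some day arithmetic.

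**1. By-visit counts do not give an ever-crossed count.** If a, b and c subjects in an arm exceed a threshold at Day 3, EOT and PTE (the scheduled post-baseline chemistry visits in Protocol Section 9), the number who exceeded it at any of the three lies between max(a, b, c) and a + b + c. The table does not say where. Values that never enter a window are additional.

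**2. Days with no window after treatment.** Inputs: EOT is on the day of the last dose or up to 2 days later; PTE is Day 21 ± 2, so Day 19 to 23 (SAP Table 3).

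| Last dose | EOT window | Days before PTE with no window | Length |
|---|---|---|---|
| Day 7 | 7–9 | 10–18 | 18 − 10 + 1 = 9 days |
| Day 10 | 10–12 | 13–18 | 18 − 13 + 1 = 6 days |
| Day 14 (bacteremia) | 14–16 | 17–18 | 18 − 17 + 1 = 2 days |

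This assumes that the on-treatment analysis days in Table 3 apply only while a subject is on treatment. If Days 8–14 were analysis days for everyone, the first two stretches would shrink to Days 15–18, or 4 days. A draw in such a stretch enters no by-visit column. Protocol 8.17.4 expects some results at other time points.

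**3. Displacement inside a window.** The scheduled value, or failing that the earliest, is used, and central outranks local. The highest value is not selected. A higher unscheduled or local value in a window that also holds a scheduled central one is therefore not counted.

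**4. Staggered peaks.** Take ALT >3×ULN at EOT with bilirubin not yet raised, then bilirubin >2×ULN at PTE with ALT back to ≤3×ULN and ALP ≤2×ULN throughout. At EOT the bilirubin criterion fails; at PTE the transaminase criterion fails. Neither criterion set is met at one visit, so the subject is not listed.

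**5. Do the other outputs fill the gap?** Using SAP Appendix 3, for a subject normal at baseline (Grade 0):

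| Threshold | Grade reached |
|---|---|
| ALT/AST >3×ULN | at least 2 (Grade 2 is >2.5–5×ULN) |
| ALT/AST >5×ULN | at least 3 |
| ALT/AST >10×ULN | 4 |
| Bilirubin >1.5× or >2×ULN | at least 2 (Grade 2 is >1.5–2.5×ULN) |

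Every value that could enter the threshold table is thus a rise of 2 grades or more. The 2-grade count is not tied to a visit, but the SAP does not say whether it uses unscheduled values. It cannot separate ALT >3×ULN from 2.5–3×ULN, or bilirubin >2×ULN from 1.5–2×ULN, and it treats each test separately. The shift tables by grade are again by visit. Worst-value statistics are in SI units and give a mean, median and range, not the number above a ULN multiple.

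**6. Scale.** 200 subjects over 5 arms is 40 per arm, so one subject is 1/40 = 2.5 percentage points. The share is larger on the baseline-normal denominator.

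**The case against.** A reader might infer that liver peaks between scheduled draws are missed by the plan altogether. The documents do not support that. Worst-value statistics include unscheduled visits, subjects with a 2-grade rise are counted and listed, and all local and central results are listed with flags. The staggered case in step 4 would meet the 2-grade criterion for both tests if normal at baseline; what is absent is anything that pairs them.

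A reader might also infer that a local ALT >5×ULN drawn between Day 3 and EOT goes uncounted. That is not established. SAP Table 3 makes each on-treatment Study Day an analysis visit, SAP 5.4 admits an unscheduled value where no scheduled one exists, and SAP 8.5 admits a local value where no central one exists. On those rules the draw may well be counted, although the SAP does not say which day columns will be printed. Nor does the same-visit wording exclude an unscheduled visit from the Hy's law listing.

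The 26% ALT figure needs its context. The same bullet gives a post-baseline change of about 30 IU/L and calls the regimen safe and well tolerated. From a value at or below ULN, a 30 IU/L rise exceeds 3×ULN only if ULN + 30 > 3×ULN, that is ULN < 15 IU/L. The documents give no ULN, but the figure is not evidence of threshold crossings.

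Finally, SAP 8.5 ties clinically notable laboratory values to the toxicity grades, so the ULN-multiple table does not plainly breach Protocol 12.6.1. It only falls short of the standard that section sets for similar values.

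What is left after these points is the missing overall incidence, the off-window and displaced values, and the concurrency rule for Hy's law.

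**Conclusion.** The point holds as a modest gap in the safety presentation. No planned output gives the per-arm incidence of ever crossing the stated ULN multiples, and none identifies a subject with non-concurrent transaminase and bilirubin peaks as a possible Hy's law case. No data are lost and no efficacy result is affected.

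How many subjects this touches cannot be derived from the documents; it depends on how many off-schedule draws are taken and when. The 2.5-point scale assumes equal allocation of 200 subjects, which the adaptive design may change. The unwindowed stretch of 2 to 9 days between EOT and PTE rests on the reading of Table 3 given above. Long intervals with no draw at all are a sampling matter that reporting cannot repair.

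**What to change.** Make three changes to SAP 8.5:

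1. Add an any-post-baseline row to the ALT/AST and bilirubin threshold table, using the worst-value rule already in SAP 5.4 and 8.5 (central, local and unscheduled values) and keeping the baseline-normal denominator. This brings the table into line with Protocol 12.6.1 and with the treatment of vital signs in SAP 8.6.
2. Widen the Hy's law listing to every subject with peak ALT or AST >3×ULN and peak bilirubin >1.5×ULN or >2×ULN at any post-baseline time. Show dates and ALP, and flag those meeting the criteria at the same visit so that the present listing remains identifiable.
3. State that the count and listing of 2-grade increases use all post-baseline values, including unscheduled ones.

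The cost is one table row, one wider listing and one sentence, all from data already collected. The downside is a few extra cases to review, some of which may prove not to be hepatic.

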### 8.6 Vital Signs

Vital signs will include blood pressure (diastolic and systolic) and heart rate and will be collected at Screening, Days 1, Day 3, Day 7, Day 10 and at EOT, PTE and FFU visits. On Day 1, blood pressure and heart rate is recorded within 30 min before, and 1 hour ( $\pm$  15 minutes) after and 3 hours ( $\pm$  15 minutes) after the completion of the first dose.

Body temperature is recorded at all visits.

Additionally, height will be collected at the Screening visit, and body weight will be collected at the Screening, EOT and FFU visits.

Blood pressure (systolic and diastolic) and heart rate will be summarized by time point and treatment group and for the minimum and maximum post-baseline values using descriptive statistics, for both the actual values and the change from baseline. Temperature will be summarized by descriptive statistics including change from baseline) by time point

Figures (line graphs) of observed values for heart rate, systolic and diastolic blood pressure over time will also be provided by treatment group.

Post-baseline vital signs will be defined as CN if they meet 1) the criterion value at the given visit, or 2) meet both the criterion value and the change from baseline criterion listed in Table 11. The incidence of CN vital signs will be summarized by time point and treatment group and will be listed and flagged in by-subject listings. An overall post-baseline incidence of CN values for each vital sign parameter, will also be summarized. A separate listing will be provided of subjects with values for a vital sign noted as CN.

0293 Version: 1.0 Status: Approved Approved Date: PTK0796-AP-17202 Statistical Analysis Plan

Omadacycline (PTK 0796)

Paratek Pharma, LLC

PTK0796-AP-17202 Statistical Analysis Plan

Vital Sign Parameter	Flag	Criterion Value	Change from Baseline
Systolic Blood Pressure	High (CH)	≥ 180	Increase of $\geq 20 \text{ mmHg}$
(mmHg)	Low (CL)	≤ 90	Decrease of ≥ 20 mmHg
Diastolic Blood Pressure	High (CH)	≥ 105	Increase of ≥ 15 mmHg
(mmHg)	Low (CL)	≤ 50	Decrease of $\geq 15 \text{ mmHg}$
	High (CH)	≥ 120	Increase of $\geq 15$ bpm
Heart Rate (bpm)	Low (CL)	≤ 5 0	Decrease of $\geq 15$ bpm

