## 5.2 Definitions

In Table 2 general definitions are provided used in the statistical analysis.

Variable	Definition		
Baseline	Unless otherwise stated, baseline is defined as the value closest to but prior to the initiation of test article administration.		
Change from baseline	Change from baseline will be defined as the post-baseline value minus the baseline value (on a subject level). Change from baseline will only be calculated for subjects who have both baseline and at least one post-baseline value for any parameter.		
Duration Variables	Duration variables will be calculated using the general formula:		
	Duration (days) = End date - Start date + 1		
	If applicable, where time is collected:		
	Duration (hh:mm) = End datetime - Start datetime		
Calculated Creatinine Clearance (mL /min),	(140 – age [yrs]) * weight [kg] * Z	Z = 0.85 for Female subjects	
Cockcroft-Gault equation	Creatinine [mg/dL] * 72		
Body Mass Index (BMI)	$BMI = Weight (kg) / Height (m)^2$		

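### The rule for a clinically notable vital sign reduces to the criterion value alone, so the change-from-baseline column of SAP Table 11 can never alter a flag

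*SAP*

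**What the plan says.** SAP 8.6 sets the rule in two limbs. Post-baseline vital signs are "defined as CN if they meet 1) the criterion value at the given visit, or 2) meet both the criterion value and the change" criterion. The second limb in full reads: "or 2) meet both the criterion value and the change from baseline criterion listed in Table 11". Table 11 then gives, for systolic pressure, diastolic pressure and heart rate, a high and a low criterion value, each paired with a required change. High heart rate, for example, is 120 bpm or more, paired with a rise of at least 15 bpm. Low systolic pressure is 90 mmHg or less, paired with "Decrease of ≥ 20 mmHg".

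The results are reported as one flag. "The incidence of CN vital signs will be summarized by time point and treatment group", together with an overall post-baseline incidence, flags in the by-subject listings and a separate listing. Nothing says that the two limbs are tabulated apart, and subjects already past a cut-off before dosing are not excluded.

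Under SAP 5.2, "baseline is defined as the value closest to but prior to the initiation of test article administration". On Day 1, blood pressure and heart rate are read within 30 minutes before dosing, and again 1 and 3 hours "after the completion of the first dose". Protocol 12.6.1 leaves the clinically notable criteria to the SAP and gives no rule of its own.

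**The concern.** A table that pairs each cut-off with a required change suggests that the change is meant to do something. Joined by this *or*, it does nothing. A programmer who codes the sentence gets value alone. One who codes the table may require both conditions. The two safety tables would differ, and the SAP as written does not tell a reader of the report why the change column exists.

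The setting makes the distinction useful. Subjects have acute pyelonephritis, and fever with chills is one of the qualifying presentations (Protocol 6.2, criterion 3). The first post-baseline readings are taken within hours of entry, when an abnormality caused by the infection may persist. An incidence that cannot separate onset from persistence is hard to interpret.

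The laboratory section is better anchored. SAP 8.5 reports increases of at least 2 grades from baseline, and elevated transaminases and bilirubin among subjects who were normal at baseline.

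**Working it through.** The documents give no figure for this rule, so there is none to reproduce.

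**1. Logic.** Let V mean that the post-baseline value meets the criterion value, and C that the change criterion is met. The written rule is V or (V and C).

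| V | C | Written rule | V and C |
|---|---|---|---|
| no | no | no | no |
| no | yes | no | no |
| yes | no | **yes** | no |
| yes | yes | yes | yes |

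The written-rule column is identical to V. An exhaustive check over whole-number baseline and post-baseline pairs, with the Table 11 cut-offs and both high and low flags, agrees. The written rule differed from value alone in 0 of 51,842 systolic, 0 of 20,402 diastolic and 0 of 42,632 heart-rate evaluations.

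**2. What is pooled under one flag (heart rate, high).**
- 100 to 122 bpm: value met, rise of 22. Flagged under either definition.
- 108 to 122 bpm: value met, rise of 14. Flagged only because change is ignored.
- 135 to 122 bpm: value met, fall of 13. Flagged although the reading has improved.

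**3. Illustrative size, no drug effect.** All inputs are assumptions, because the documents give no heart-rate distribution: normal, baseline mean 92 bpm, SD 18 at both times, correlation 0.7, and a 3 bpm fall, so the post-dose mean is 89. One post-baseline reading is considered.
- Value alone: P(V) = 1 − Φ((120 − 89)/18) = 1 − Φ(1.722) = 4.25%.
- Change: mean −3, SD = 18 × √(2 − 2 × 0.7) = 13.94. The threshold is (15 + 3)/13.94 = 1.291. The correlation of change with the post-dose value is 18 × (1 − 0.7)/13.94 = 0.387.
- Value and change: the bivariate normal upper tail at (1.722, 1.291) with correlation 0.387 is 1.31%.
- Value met and baseline already ≥120: the baseline threshold is (120 − 92)/18 = 1.556. The upper tail at (1.722, 1.556) with correlation 0.7 is 1.97%.
- Share of value-only flags without a 15 bpm rise: (4.25 − 1.31)/4.25 = 69%.
- Share already ≥120 at baseline: 1.97/4.25 = 46%.

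The last two shares differ because some subjects cross 120 from below with a rise of less than 15 bpm.

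With about 200/5 = 40 subjects per arm before any reallocation, the expected number flagged at one reading is 40 × 0.0425 = 1.7 by value alone and 40 × 0.0131 = 0.5 by both.

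**4. Range.** Simulation of 400,000 subjects per scenario used mean 90 to 105 bpm at both times, SD 16, correlation 0.5 to 0.85 and no drug effect. It gave 3.0% to 17.4% flagged by value alone and 0.4% to 7.1% by both. Between 20% and 68% of the value-only flags were already ≥120 at baseline.

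**5. Effect on an arm contrast.** Add an assumed 15 bpm drug effect to the inputs of step 3, so the post-dose mean is 104.

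| Definition | No effect | +15 bpm | Difference | Ratio |
|---|---|---|---|---|
| Value alone | 4.25% | 18.70% | 14.45 points | 4.4 |
| Value and change | 1.31% | 12.00% | 10.69 points | 9.2 |

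With the effect, 4.45/18.70 = 24% of value-only flags were already ≥120 at baseline.

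**The case against.** The strongest reply is that 1) and 2) are two nested tiers, as with the two nested Hy's law definitions in SAP 8.5. That is possible. But the Hy's law definitions are joined by *and*, while 8.6 uses *or* and then reports one incidence. The documents do not settle which was intended, and they do not show that requiring both conditions was meant to be the main definition. This limits the fix to reporting both tiers.

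A second reply also stands: change from baseline is not lost. SAP 8.6 summarizes it descriptively for blood pressure and heart rate by time point and treatment group, and for the minimum and maximum post-baseline values. A shift in heart rate would be visible there.

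A reader might infer three stronger conclusions that the documents do not support:
- *That baseline abnormality is counted as a drug finding.* The flag applies only to post-baseline values and is called clinically notable, not drug-related. A baseline abnormality counts only if the cut-off is met again after dosing.
- *That the rule dilutes the difference between arms.* Step 5 shows a larger absolute difference under value alone; only the ratio is smaller. Randomization should balance abnormality at entry on average. The +15 bpm input is also borrowed: Protocol 7.4 gives it for 200 mg over 60 minutes, whereas this trial infuses over 90 minutes, and three of the four omadacycline groups receive 200 mg iv only on Day 1.
- *That arm decisions rest on this flag.* SAP 3.4 bases them primarily on safety and tolerability and refers to the DMC charter, which is not among the documents. Nothing ties Table 11 to those decisions, and SAP 3.5 places the analyses in the SAP after the end of the study.

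**Conclusion.** The point holds as a defect of definition. As written, SAP 8.6 flags on value alone and Table 11's change column is inert; that follows from the wording without assumptions. The consequence is one incidence that cannot distinguish new or worsened abnormalities from persistent ones. In the illustration, the no-effect rate is about three times as high by value alone as by both conditions (4.25% against 1.31%), and just under half of the value-only flags were already past the cut-off at baseline. These sizes rest entirely on the assumed heart-rate distribution and vary widely over the range shown. They are for a single reading, not the overall post-baseline incidence.

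The defect is confined to a descriptive safety summary. It does not touch the efficacy analyses and is not shown to bias the comparison between arms. It is worth correcting because the stated rule cannot use its own table and the correction is very cheap.

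**What to change.** Replace the *or* sentence in SAP 8.6 with two labelled tiers: (a) criterion value met; (b) criterion value and change-from-baseline criterion both met. Tabulate both by time point and for the overall post-baseline incidence, and show which tier applies in the by-subject flags and the separate listing. This makes the change column operative without deciding which tier was meant to be primary.

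The cost is one sentence in the SAP, one programming condition and one extra row per parameter in the tables. No new data are needed, since the baseline value is already collected and defined. The change should be made before database lock, the point by which SAP 3.5 requires amendments to be approved.
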